# 5.5 Labelling

Primary and Secondary packaging for the IMP will be prepared according to Annex 13 of GMP (Good Manufacturing Practice) European directive (Eudralex Volume 4), The information that will be included in the final labels are reported in the examples below in English.

[figure not shown]
As per guidelines, labels of the primary and secondary packaging will be translated in the investigational site local language.

Primary Packaging (powder and buffer vial):

### Secondary Packaging (outer box)

# 5.6 Handling and storage of IMP at the Site and IMP Accountability

The kit for the preparation of [ $^{68}$ Ga]-NeoBOMB1 should be stored upon receipt at 5°C ± 3°C in a temperature-controlled refrigerator.

Regulation on how medication labelled with "For clinical trial use only" is managed:

- Dispensary on pharmacy/investigator (if applicable)
- Written receipt
- Storage at the trial centers
- Documentation of the dispensing to the patients and their usage
- Return of unused medication and empty containers
- Procedure and documentation of the return to the Sponsor or the destruction of remainders

The Investigators will be responsible for ensuring the correct storage and sufficient stocks of the IMP and comparative drug at the trial centres. The Investigator bears the responsibility for the proper storage in a secure location at the site which means in a lockable cabinet with restricted access to the Investigator(s) and authorized site staff. Personnel having access to the IMP will be listed on the Authorization and Delegation log in the Investigator Site File (ISF). The Investigators will ensure that the IMP is only used according to this protocol. The Investigator will be responsible for the Drug Accountability log. Drug accountability will be noted by a monitor during site visits and at the completion of the trial. The Drug manufacturer will provide the clinical trial centre with appropriate forms to document shipments, receipt and return (or destruction) of the product.

Unused kits for preparation of [Ga]-NeoBOMB1 will be returned to the manufacturer or destroyed as per the local procedures.

Based on the stability tests performed, the NeoBOMB1 kit can be stored upon receipt at  $5^{\circ}C \pm 3^{\circ}C$  until the expiry date stated on the labels.

# 5.7 Subject compliance

Due to the nature of the drug, patient's compliance about dosing is of no concern.

# 6 Safety Definitions and Reporting Requirements

Safety assessments will consist of monitoring and recording AEs, including SAEs.

# 6.1 Adverse Events (AEs)

An adverse event (AE) is defined as any untoward medical occurrence in the form of signs, symptoms, abnormal laboratory findings, or diseases that emerges or worsens relative to baseline during a clinical study with an investigational product, regardless of causal relationship and even if no investigational product has been administered.

Adverse events include:

- Worsening or increase in frequency or intensity of a pre-existing disease or medical condition
- Abnormal laboratory tests

Adverse events do not include:

- Pre-planned interventions/hospitalizations
- Medical or surgical procedures, e.g. surgery, endoscopy, tooth extraction, transfusion. However, the event leading to the procedure is an AE. If this event is serious, the procedure must be described in the SAE narrative.
- Pre-existing disease or medical condition that does not worsen.
- Diagnosis of progressive disease i.e. increase in tumour load or newly identified metastasis/complication during routine diagnostic CT.
- Overdose of either study drug or concomitant medication without any signs or symptoms that should be considered only as a specific situation.

All AEs will be reported and recorded from the signature of the ICF.

# 6.2 Serious Adverse Events (SAEs)

A serious adverse event (SAE) is defined by the International Conference on Harmonization (ICH) guidelines as any AE fulfilling at least one of the following:

• Resulted in deaths

- Was life-threatening defined as an event in which the subject was, in the judgment of the investigator, at risk of death at the time of the event; it does not refer to an event that hypothetically might have caused death if it had been more severe
- **Required or prolonged hospitalization:** i.e. the AE requires at least a 24-hour inpatient hospitalization or prolongs a hospitalization beyond the expected length of stay. Hospital admissions for surgery planned before trial entry, for social reasons or for normal disease management (including treatment adjustment) are not to be considered as SAE according to this criterion.
- **Resulted in persistent or significant disability or incapacity** (i.e. a substantial disruption of a person's ability to conduct normal life functions)
- Was a congenital anomaly or birth defect: i.e. an adverse outcome in a child or foetus of a subject's partner exposed to the study drug, before conception or during pregnancy.
- is medically significant, i.e. an event may not be immediately life-threatening or result in death or hospitalization but may jeopardize the subject or may require intervention to prevent one of the other outcomes listed in the above definition should also usually be considered as serious.

Inpatient hospitalization is defined as an overnight stay in a hospital unit and/or emergency room that includes at least one night (midnight to 06:00 AM).

The following is not considered as a SAE and should be reported as an AE only:

• Treatment of an emergency or outpatient basis for an event not fulfilling the definition of seriousness given above and not resulting in hospitalization

The following reasons for hospitalization are not considered as AEs or SAEs:

- Standard monitoring of a pre-existing disease or medical condition that did not worsen, e.g. hospitalization for coronary angiography in a subject with stable angina pectoris
- Elective treatment of a pre-existing disease or medical condition that did not worsen, e.g. hospitalization for chemotherapy for cancer, elective hip replacement for arthritis
- Hospitalization for cosmetic elective surgery, social and/or convenience reasons

# 6.3 Adverse Drug Reaction (ADR) & Unexpected Adverse Drug Reaction

An ADR is any noxious and unintended response to an IMP related to any dose with at least a reasonably possible causal relationship with the IMP. Briefly, an ADR is an AE which is possibly related to IMP by either the investigator or the study sponsor.

# 6.4 Suspected Unexpected Serious Adverse Reaction (SUSAR)

Unexpected ADR means the nature or severity of which is not consistent with the applicable product information available for the IMP. Expected ADRs are listed in the Investigator's Brochure

A SUSAR is an adverse event, the nature or severity of which is not consistent with the applicable information available in the reference documents available for the IMP and is regarded as serious, and has at least possible relationship with the IMP.

# 6.5 Pregnancy

To avoid the application of the study medication during pregnancy, pregnancy tests will be performed at Screening and prior to injection. Any pregnancy that occurs during study participation must be reported to the investigator/sponsor immediately (no later than SAEs reporting timelines). If a pregnancy should be confirmed after informed consent has been obtained but prior to the initiation of the study drug, the patient must be excluded from the trial. The pregnancy must be followed up to determine outcome (including premature termination) and status of mother and child. Pregnancy complications (including spontaneous abortions) and elective terminations must be reported as an AE or SAE.

Any SAE occurring in association with a pregnancy brought to the investigator's attention after the subject has completed the study and considered by the investigator as possibly related to the IMP, must be promptly reported to the sponsor.

As the consent for the study does not cover the consent for the follow-up of the pregnancy, a separate consent must be obtained.

# 6.6 Severity of adverse events / Grading

Intensity of all adverse events will be graded according to the Toxicity Grading Scale vaccine clinical trials (Appendix 2) and reported in detail in the Case Report Form (CRF). Adverse events not listed in the Toxicity Grading Scale vaccine clinical trials should be graded as follows:

CTC grade	Equivalent to	Definition
Grade 1	Mild	Discomfort noticed but no disruption of normal daily activity and does not require mandatory corrective/symptomatic
		treatment
		Discomfort sufficient to reduce or affect daily activity; no
Grade 2	Moderate	treatment or medical intervention (other than minimal) is
	Moderate	indicated although this could improve the overall wellbeing
		or symptoms of the patient.
	Severe	Inability to work or perform normal daily activity; treatment
Grade 3		or medical intervention is indicated to improve the overall
Grade 5	Severe	wellbeing or symptoms; delaying the onset of treatment is
		not putting the survival of the patient at direct risk.
	Life-	An immediate threat to life or leading to a permanent
Grade 4	threatening /	mental or physical condition that prevents work or
	disabling	performing normal daily activities; treatment or medical
	usabiing	intervention is required to maintain survival.

Grade 5 Death	AE resulting in death
---------------	-----------------------

# 6.7 Relationship to study drug

The assessment of relationship of adverse events to the administration of IMP is a clinical decision based on all available information and considering all relevant factors such as (but not limited to) the underlying indication, coexisting diseases, concomitant medication, etc. at the time of the completion of the case report form.

Is there a reasonable possibility that the study drug caused the event?

Answer **YES** (definitely, probably or possibly related) if one or more of the following criteria apply:

- The event follows a reasonable temporal sequence from administration of study drug.
- The event could not be reasonably attributed to the known characteristics of the patient's clinical state, environmental or toxic factors or other modes of therapy administered to the patient.
- The event follows a known pattern of response to study drug.

The event disappears or decreases on cessation or reduction in dose of the study drug. (It should be noted that in some situations an AE will not disappear or decrease in intensity upon discontinuation of study drug despite other clear indications of relatedness).

Otherwise answer **NO** (unlikely, probably not related or definitely not related).

# 6.8 Reporting procedures for AEs

A special section is designated to adverse events in the CRF where the following details must be entered:

- Type of adverse event (diagnosis or syndrome; if not known signs or symptoms) and brief description (including context of occurrence)
- Start (date)
- End (date)
- Severity (mild, moderate, severe, life-threatening/disabling, death)
- Serious (no / yes)
- Outcome (resolved, ongoing, ongoing improved, ongoing worsening) and recovery date
- Action taken (none, study medication dose reduced, study medication interrupted, study medication discontinued, medication therapy, surgical procedure, hospitalization, other)
- Relation to study drug (possibly, probably or definitely related or unlikely, probably not related or definitely not related)
- Treatment date with the IMP (in order to estimate the time to onset)

• Patients relevant medical history and/or concomitant treatments that may provide alternative explanation regarding the AEs occurrence.

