## 4.1.2 Physical examinations

Physical examinations will be performed at all visits except at Day 2 for patients included in the non-dosimetry group. All of them will be performed by trained medical personnel only, prior to IMP administration on the dosing day. Any abnormal findings will be recorded as AEs. Furthermore, auscultation of lungs and heart and palpation of abdomen will be performed

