### 4.2.2 Injection/PET Imaging day (Day 1/Visit 1)

### Before administration

Hospitalization will occur on the day of administration of [68Ga]-NeoBOMB1.

For all patients, the following study assessments will be performed on the day of administration of [Ga]-NeoBOMB1:

- Participant will be asked to drink 750 ml of water within 1h before image acquisitions
- Control of dated informed consent
- Review of inclusion and exclusion criteria
- Control of adverse events and concomitant medications
- Physical examination: weight, auscultation of lungs and heart, oral inspection, abdominal palpation
- Vital signs: blood pressure, heart rate
- 12-lead ECG including frequency-corrected QT-time
- Haematology, Blood chemistry, Coagulation parameters: Quick, INR, aPTT, fibrinogen, Urinalysis
- Urine dipstick pregnancy test (in women of childbearing potential)
- Venous blood sampling (~1 ml) for radioactivity assay (only for dosimetry group)
- Urine collection for radioactivity assay (only for dosimetry group)
- Histopathologic evaluation
- Concomitant medications can be administered from 4h after the [Ga]-NeoBOMB1 administration.

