# 6.9 Reporting procedures for SAEs

When an SAE is made known to the Principal Investigator (PI) or other site personnel, it must be reported to AAA Pharmacovigilance within the best timelines and no more than 24 hours (one calendar day) of knowledge of the event.

The responsibilities of the PI include but are not limited to:

- Identifying the SAE (detailed description) and providing the criteria of seriousness,
- Assessing causality/relationship of the SAE to investigational product,
- Determining the severity/intensity according to the protocol and event outcome,
- Determining the event onset and resolution dates,
- Maintaining adequate documentation of the SAE and all communications relating to the event including communications with the subject, treating physician, AAA Pharmacovigilance, CRO

The SAE reporting process is described below:

- Complete an SAE report form. The SAE report form must be documented in English and any supporting documentation (e.g. event narrative or discharge summary) must be briefly summarized in English in the SAE report. Unless otherwise requested by AAA Pharmacovigilance, only death certificates and autopsy reports may be submitted as separate documents. Discharge summary translated in English may also been provided upon Sponsor (AAA) request
- Provide as much information as is known at the time the initial report is submitted to AAA Pharmacovigilance. The elements required to make an initial assessment of the event to meet reporting obligations to health authorities are:
  - ✓ Site number (4-digit) and subject number (3-digit) and subject initials (if local privacy laws allow),
  - ✓ Serious event description plus all seriousness criterion that apply (e.g., hospitalization, etc),
  - ✓ Relationship to investigational product (causality assessment),
  - ✓ Severity/intensity grade as available,
  - ✓ Start date of event,
  - ✓ Investigational product administration details (i.e., dose, regimen, and therapy dates),
  - ✓ Outcome at time of initial reporting
  - ✓ Reporter name, Investigator name, phone number, and email address.
- Fax or email the completed SAE report form to AAA Pharmacovigilance using the fax number or email address located on the SAE report form or in the SAE Completion Guidelines (Fax: \_\_\_\_\_\_, E-mail: \_\_\_\_\_\_).

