# 6.11 Adverse Event Reporting Period

All AEs will be reported and recorded from the signature of the ICF.

Investigators will seek information on AEs at each patient contact throughout the trial. All AEs, whether reported by the patient or noted by study personnel, will be recorded in the patient's medical record and on the Adverse Event part of the application day Case Report Form (CRF).

After informed consent has been obtained all AEs and SAEs regardless of relationship to the study drug will be reported until FU3 or until the event has resolved to baseline grade or better, the event is assessed as stable by the investigator, the patient is lost to follow-up, or the patient withdraws consent.

After FU3, investigators should report any deaths, SAEs, or other AEs of concern that are believed to be related to prior treatment with the study drug.

Any Serious Adverse Event (SAE) that is ongoing at the time of FU3 should be followed-up until resolved.

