#### 5.4 Handling of Missing Data

Missing/Partial Dates:

- In cases of incomplete dates (e.g. AEs and concomitant medications), the missing component(s) will be assumed as the most conservative value possible. No imputation of start/end dates or times will be performed.
  - If a medication date or time is missing or partially missing and it cannot be determined whether it was taken prior or concomitantly, it will be considered both a prior and a concomitant medication.
  - If the partial AE onset date/time information does not indicate that the event started prior to or after the treatment, the event will be classified as treatment-emergent.

- Time from first diagnosis of primary cancer (months) is calculated as (date of administration of the study drug date of first diagnosis + 1)/30.4375. If the month and year of the first diagnosis are provided but the day is missing, the missing day is imputed as 15. If only the year is provided, then the missing month and day are imputed as July 1st for the calculation.
- Actual data values as they appear in the original case report forms (CRFs) will be presented in the data listings.

Other Missing Values: Missing values for other individual data points will remain as missing unless otherwise specified. Missing values will not be imputed and only observed values will be used in data analyses and presentations unless otherwise stated.

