#### 8.1 Adverse Events

AEs will be coded using MedDRA version available at the time (updated biannually).

Treatment-emergent adverse events (TEAEs) are defined as AEs that start on or after the initiation of IMP administration.

Intensity of all adverse events will be graded according to the Toxicity Grading Scale in vaccine clinical trials. Adverse events not listed in the Toxicity Grading Scale in vaccine clinical trials should be graded as guided in study protocol.

An overview of AEs will be provided which summarizes subject incidence of the following information:

- Any TEAEs,
- Drug-related TEAEs,
- Grade 3/4/5 TEAEs,
- Drug-related grade 3/4/5 TEAEs,
- Deaths due to AEs,
- Treatment-emergent SAEs,
- Drug-related treatment-emergent SAEs,
- Dose interruption due to TEAEs, and
- Dose interruption due to drug-related TEAEs.

The number and percentage of subjects with TEAEs will be summarized by SOC and PT. Drugrelated TEAEs, treatment-emergent SAEs, drug-related treatment-emergent SAEs, TEAEs leading to dose interruption of study drug, and drug-related TEAEs leading to dose interruption of study drug will be summarized in the same manner. For these summaries, subjects with multiple adverse events will be counted only once per SOC and PT. Note that drug-related AEs include the AEs which either definitely, probably, or possibly related to study drug.

Summaries will be provided by the worst toxicity grade, SOC, and PT for the number and percentage of subjects with TEAEs and drug-related TEAEs. For these summaries, subjects with multiple adverse events will be counted only once by the worst toxicity grade within each SOC and PT.

Data listings will be provided for SAEs, grade 3/4/5 AEs, AEs leading to dose interruption, Hypersensitivity (SMQ) AEs, and AEs leading to death. A by-subject AE data listing including, but not limited to, verbatim, PT, SOC, toxicity grade, action taken, outcome, and relationship to study drug will be provided.

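### Protocol 6.8 and 6.9 require only calendar dates for AE onset, so the SAP default can count an AE that began on Day 1 before the injection as treatment-emergent

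*Protocol*

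**What the plan says.** Protocol 6.8 lists the details that have to be entered for every AE. Onset and end are each specified as a date, and the injection appears as "Treatment date with the IMP (in order to estimate the time to onset". No clock time is listed for either. Section 6.9 is similar for SAEs: it asks for "Start date of event" and "Investigational product administration details (i.e., dose, regimen, and therapy dates".

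Collection begins at consent. Section 6.11 states: "All AEs will be reported and recorded from the signature of the ICF". On Day 1, section 4.2.2 places "Control of adverse events and concomitant medications" before administration, together with a physical examination, vital signs, ECG and laboratory tests. Section 4.1.2 has the examination done "prior to IMP administration on the dosing day. Any abnormal findings will be recorded as AEs".

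SAP 8.1 reads: "Treatment-emergent adverse events (TEAEs) are defined as AEs that start on or after the initiation of IMP administration". SAP 5.4 adds a default. If the partial onset date/time information "does not indicate that the event started prior to or after the treatment, the event will be classified as treatment-emergent". The same section says that start and end dates and times will not be imputed.

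**The concern.** The two documents work at different resolutions. The TEAE definition turns on an instant, while the protocol requires only the day. They come apart on the injection date, which is also the day with a full round of pre-dose assessments and, for a single injection of a nuclide with a 68-minute half-life, the day of most of the exposure. A new abnormality picked up that morning is background, but dates alone cannot keep it out of the treatment-emergent tables.

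Safety and tolerability is a secondary objective. The tables at stake are the all-cause ones in SAP 8.1: any TEAE, grade 3/4/5 TEAEs, treatment-emergent SAEs and the SOC/PT summaries. SAP 8 presents them by tumour type as well as in total.

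**Working it through.** The plan states no figure on this point, so there is none to reproduce. The check applies the plan's own rules to example onsets.

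**Step 1. Rules.** SAP 5.1 sets study day = event date − injection date + 1 on or after the injection date, and event date − injection date before it. SAP 8.1 sets TEAE = yes if onset is at or after the start of administration. With dates only, an onset on the injection date satisfies a date-level reading of on or after. If the order is instead treated as undetermined, the SAP 5.4 default applies. Both routes give TEAE = yes.

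**Step 2. Example.** Assume an injection at 11:00 on Day 1.

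| Onset | Date difference | Study day | TEAE from dates | Hours from injection | TEAE from date-time |
|---|---|---|---|---|---|
| Day before, 08:00 | −1 | −1 | no | −27.0 | no |
| Day 1, 08:30 | 0 | 1 | yes | −2.5 | no |
| Day 1, 11:05 | 0 | 1 | yes | 0.08 | yes |
| Day 1, 11:30 | 0 | 1 | yes | 0.5 | yes |
| Day 1, 15:00 | 0 | 1 | yes | 4.0 | yes |

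Only the second row is misclassified. Events dated before Day 1 are correctly excluded, and events after the injection are correctly included.

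**Step 3. Which events are exposed.** Four conditions must all hold. The event must be new or worsened (protocol 6.1 excludes pre-existing conditions that do not worsen). It must start on the injection date. It must start before the injection. Nothing else recorded may show the order.

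**Step 4. Effect per patient.** A misclassified patient with no other TEAE raises the any-TEAE percentage by 1/50 = 2 points overall, and by 1/10 = 10 points within a tumour type of 10.

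**Step 5. Number of patients.** The documents give no rate. For an assumed share p of patients with such an event, the expected number is 50p: 1, 2.5 and 5 patients for p = 2%, 5% and 10%. These shares are illustrative only, and the counts assume that no order was recorded for any of the events.

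**The case against.** The strongest reply is that the eCRF is not among the documents. Section 6.8 says what must be entered, not that the form holds nothing else. SAP 5.4 speaks of AE onset date/time and of not imputing times, which suggests that its authors expected a time to be available. This stands. A reader might infer that the AE form records dates only, but the documents show only that the protocol requires no more than dates.

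A reader might also infer that every AE arising on Day 1 before the injection becomes a TEAE. That goes too far. Section 6.8 requires a brief description with the context of occurrence, which may show the order. The visit schedule in 4.5 has a combined row for baseline findings and AEs, so some pre-dose abnormalities may be entered as baseline findings. An abnormality that began earlier should carry an earlier date.

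The SAP 5.4 default is deliberately conservative, and that is a sound choice for the occasional missing time. It is less suitable where the time was never required. Drug-related TEAEs are tabulated separately, and the causality criteria in protocol 6.7 include temporal sequence, so an investigator who knows that an event came first can mark it unrelated. This limits the damage to the all-cause tables.

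A third inference would be that acute reactions, including those in the hypersensitivity listing, cannot be assessed. The documents do not support this either. The SAP plans no time-to-onset analysis, dates do allow an estimate in days, vital signs are monitored during the bolus, and the by-subject AE listing carries the verbatim term, action taken and relationship.

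Finally, the injection time is probably recorded, because samples and scans are timed from it. That helps only if there is an onset time to compare with it.

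**Conclusion.** The concern holds in limited form. The protocol requires calendar dates, the SAP's definition needs the order within Day 1, and the SAP default resolves an unknown order in one direction. All-cause TEAE counts, and possibly grade 3/4/5 counts, are therefore biased upward by any Day 1 pre-injection event whose order is not otherwise recorded. The bias is probably modest and its size cannot be derived from the documents. The 2% to 10% shares above are assumptions, and a reader should not take them as evidence of a materially inflated TEAE rate.

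The conclusion assumes that the eCRF has no mandatory onset time and that the other protocol versions named in SAP section 1 (2.0 and 3.1), which are not available here, do not add one. If the eCRF does hold a time, what remains is a mismatch of wording between protocol and SAP.

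**What to change.** In protocol 6.8 and 6.9, require the onset clock time, or at least a flag for before or after injection, for any AE starting on Day 1, and link it to the recorded injection start time.

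In SAP 8.1, state that TEAE status on Day 1 is set by date and time, and that a new event documented at the pre-dose check is not treatment-emergent unless it worsens after the injection. State also that the SAP 5.4 default applies only when the time or order is truly unknown.

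The cost is one extra field for Day 1 events and a few sentences of text. It is best done before data collection, since onset times are hard to recover later; for events already collected, a before/after flag taken from source notes would be enough. SAP section 1 allows revision up to database lock. If the eCRF already captures the time, only the wording needs aligning. Reporting onset in minutes or hours is optional and no planned output depends on it.
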